Sample size calculations for this study are challenging because of the lack of a gold standard test, and the fact that prevalence in the study population is both unknown and increasing over time. The following calculations assume that the HPA laboratory-based test is 100% sensitive and 100% specific, which is known not to be the case. The calculations are therefore no more than illustrative. We assumed that the true sensitivity and specificity of the HTK are both 98%. These are the minimum values currently considered acceptable by the MHRA (18/04/2020). The performance metric of the most interest is the PPV, defined as the probability that a person who tests positive does in fact have antibodies. Table 2 shows the expected 95% confidence intervals for sensitivity, specificity and PPV which would be obtained for a sample size of 1000 or 2500 participants, under various assumed values of prevalence in the study population. If we were to consider 90% PPV acceptable, and prevalence in the study sample was 20%, we would require 2,500 participants to obtain a 95% CI which was wholly above 90% PPV.

Evaluating Detection of SARS-CoV-2 antibodies using home test kits (EDSAB-HOME study)

Protocol 30.05.2020 Version 04.03

Table 2 The expected 95% confidence intervals (CIs) around estimated sensitivity, specificity and PPV under potential sample sizes of n = 1000 and n = 2500, assuming true sensitivity and specificity are both 98%.

	Study size	of n = 1000		Study size of	of n = 2500	
Prevalence in study population	Sensitivity 95% Cl	Specificity 95% CI	PPV in study population: estimate (95% CI)	Sensitivity 95% CI	Specificity 95% CI	PPV in study population: estimate (95% CI)
5%	0.93,1.00	0.97,0.99	0.72 (0.61,0.82)	0.95,1.00	0.97,0.99	0.72 (0.65,0.79)
10%	0.95,1.00	0.97,0.99	0.85 (0.78,0.91)	0.96,1.00	0.97,0.99	0.85 (0.80,0.89)
15%	0.95,1.00	0.97,0.99	0.90 (0.85,0.94)	0.96,0.99	0.97,0.99	0.90 (0.87,0.92)
20%	0.96,1.00	0.97,0.99	0.93 (0.89,0.96)	0.97,0.99	0.97,0.99	0.92 (0.90,0.95)
25%	0.96,1.00	0.97,0.99	0.94 (0.91,0.97)	0.97,0.99	0.97,0.99	0.94 (0.92,0.96)

Test performance may vary across populations, e.g. due to variation in underlying severity of disease. To allow exploration of this, initially we propose a cohort of 1500 healthcare workers and 1000 police officers, with later possible extension to the general public.

Analysis 1b

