We will also report test accuracy in comparison to locally relevant adaptations of the World Health Organisation [20th March, version 6] criteria for confirmed cases (RT-PCR positive), suspect cases (combining symptoms and exposure) and probable cases (suspect cases with inconclusive or no RT-PCR results).

Our adapted definition reflects UK screening and swabbing practice; see Appendix 2. On 5 March, the UK Government confirmed that local COVID-19 transmission was occurring. After this, it changed policy from a 'containment phase' based on active case finding and molecular screening of individuals meeting a definition based on WHO criteria to one of 'delay' in which testing was largely confined to hospitalised cases, based on limitations in testing capacity.

Our definition includes the WHO's recommended confirmed, suspect and probable cases. In addition, we are pre-specifying a category of 'symptoms but tested negative' because molecular testing may be insensitive.

Our approach will otherwise be similar to that in Analysis 1a.

Analysis 2

The key assumption of Analysis 1 (that the laboratory-based assay makes no errors) is known to be untrue. In Analysis 2, we will use the "known positive" status of up to 500 of the study participants, alongside additional data, to estimate the sensitivity and specificity of both the HTK and the laboratory-based assay.

Evaluating Detection of SARS-CoV-2 antibodies using home test kits (EDSAB-HOME study)

Protocol 30.05.2020 Version 04.03

Data from multiple sources, including the present study, will be synthesised together using a Bayesian latent class modelling / multi-parameter evidence synthesis approach.

As described on page 2, we propose additional data collection through two main routes. We will also attempt to identify as many other relevant data sources as possible. Relevant studies will be those involving the HPA assay, HPA and other assays including T-SPOT Coronavirus, HPA and the home test kit, and other assays which have been compared to HPA and the home test kit. Data from studies with each of these designs will improve estimation of the accuracy of both the HTK *and* the HPA assay. Attention will be focused on:

Other studies using two or more assays on populations with unknown prevalence. Information from studies with a wide range of different (unknown) seroprevalence values can contribute useful information about the sensitivity and specificity of the assays concerned.

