The multi-parameter evidence synthesis model, combining data across all identified data sources, will produce estimates of the sensitivity and specificity of the home test kit, the sensitivity and specificity of the HPA assay (and of any other laboratory-based assays included) and implied PPVs and NPVs across pretest probabilities.

Analyses will account for anticipated positive dependencies between test results on the HTK and other antibody tests (e.g. EuroImmun, Roche) in both antibody positive and antibody negative samples, i.e. 'conditional dependence'.

Objective 2

To describe the agreement between reading of the HTK results (i) by users of the service, (ii) by a trained professional examining a photograph, (iii) by a trained professional in a community setting - and subsequently the accuracy of user-reading in detection of anti-SARS-CoV-2 antibody

Increasingly, antibody results may be available to NHS and other staff participating in the study. This is because both NHS and private test provision is increasingly available, independent of any release by the study of antibody tests generated at Phase 1. If a human is reading the result of the HTK, their knowledge of the expected result (based on EIA results) may represent a bias in their result reading.

To assess accuracy of reading, we need to deal with this bias. There are two effective strategies available:

- The subject does not read their result; it is read by an automated process which does not know the previous status (such the NHSX app under development). This is expected to be the case with the NHSX App being built to read the product being developed by the UK-RTC.
- The subject does not read their result, but rather the result of someone else whose antibody status they do not know. This may be the case if the EDSAB-HOME investigation is applied to a product without a app reader. In this setting, we will ask groups of 2 or more individuals to set up their own tests synchronously, and during the 10-minute incubation we will relabel the tests such that the individuals do not know whose test is being read.

Two analyses of agreement will be produced, one focusing on agreement between self-read and expertread results, and between photo-read and expert read results. A second analysis will provide estimates of the overall sensitivity and specificity of self-read tests in reflecting antibody status. Both analyses will

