APPENDIX ONE

Serological responses to SARS-CoV-2:

Specificity: The specificity of a test refers to the proportion of individuals without the condition who test negative.

Humans make antibodies against coronaviruses following infection, predominantly against the Spike (S) and nucleoproteins (N) (1). Four coronaviruses circulate in the general population, and a high proportion of the population has antibodies against these HKU1, 229E, NL63 and OC43 coronaviruses (2). This is a potential challenge for antibody based tests given homology between coronaviruses; for the application proposed, a highly specific assay (i.e. one which is positive only if individuals are recently exposed to SARS-CoV-2, without false positive tests). Nevertheless, there are indications such specific detection is possible:

- Immune responses against the S1 component of the Spike protein, or the receptor-binding domain (RBD) within it, appear specific to SARS-CoV2, although responses against S2 as more cross reactive predominantly against the Spike (S) and nucleoproteins (N) (1).
- Following SARS-CoV-2 infection, IgG, IgM and IgA responses are generated against the spike protein (3); sensitivity of assays detecting IgA may be slightly higher than that of assays using IgG (2).
- Serological assays against S protein (EIA signal) are strongly correlated with neutralisation assays (2) (4).
- Commercial assays for components of SARS-CoV-2 S protein and N protein are becoming available. One example is a CE marked Enzyme Immunoassay (EIA) from Euroimmun. There are reports of a potential cross reactivity in 2/60 samples from one plasma set analysed using this kit (2), and validation work done in PHE Porton Down¹ found one strong positive and one indeterminate result in 92 samples believed to be negative (Tables 1,2 reproduce data from report cited in footnote). These observations need more investigation – the possible false positive could be investigated using a viral neutralisation assay to determine whether the plasma is in fact a true positive.
- At present, taken together, these data suggest that the EuroImmun assay has specificity in the region of 97 99%. Running larger number of known negative samples through this assay is required to obtain a more accurate estimate of specificity.
- Newer anti-N EIAs from Roche and Abbott are also available, and may be deployed in the NHS.

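### Analysis 2 names no required known-negative source, so under the dependence it allows, HTK and HPA specificity (and PPV) are bounded but not point-identified

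*Protocol*

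**What the plan says.** All of this is in the protocol, under Statistical Analysis, Objective 1, unless another place is given.

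- **Aim.** Analysis 2 drops the error-free HPA assumption of Analysis 1 and sets out "to estimate the sensitivity and specificity of both the HTK and the laboratory-based assay".
- **Known-status group.** Only known positives are named, up to 500. Study Design describes them as people with an earlier positive SARS-CoV-2 test.
- **External data.** The search is open to any study involving the HPA, alone or with other assays, T-SPOT included. The one item listed for focused attention is "Other studies using two or more assays on populations with unknown prevalence", supported by the statement that "Information from studies with a wide range of different (unknown) seroprevalence values can contribute useful information about the sensitivity and specificity" of those assays.
- **Dependence.** "Analyses will account for anticipated positive dependencies between test results on the HTK and other antibody tests", and this applies "in both antibody positive and antibody negative samples".
- **Known negatives.** Analysis 2 mentions none. Appendix One reports 92 believed-negative samples for the EuroImmun assay and says of it: "Running larger number of known negative samples through this assay is required to obtain a more accurate estimate of specificity".
- **What depends on it.** The sample size section says: "The performance metric of the most interest is the PPV". Objective 2 obtains the specificity of self-reading by multiplying by the Analysis 2 specificity. Objective 5 bases advice to users on HTK sensitivity and specificity.

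**The concern.** Populations with different unknown prevalences identify the accuracy of two tests when the tests are independent within each antibody class. The protocol gives up that independence for HTK and HPA. Known positives carry information about sensitivity and none about specificity, so the named sources leave the antibody-negative class without an anchor.

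PPV at low or moderate prevalence is driven mainly by specificity. A posterior for specificity shaped by the prior would be reported with a credible interval that looks data-based, and would pass into the PPV, the self-read specificity and the advice given to users.

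**Working it through.** **Inputs.** From the protocol: HTK sensitivity and specificity 0.98; n = 2,500; prevalence 20%; PPV benchmark 90% (sample size section). Assumed, because the protocol gives no figures: HPA sensitivity 0.95 and specificity 0.99; HTK-HPA covariance 0.008 in antibody positives and 0.003 in negatives (also tried from 0.001 to 0.009); lowest study prevalence from 0.5% to 10%.

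**1. The protocol's own figure.** PPV = Se·p / [Se·p + (1−Sp)(1−p)] = 0.196 / (0.196 + 0.016) = 0.925. Expected HTK positives: 2,500 × 0.212 = 530. Wald 95% interval: 0.925 ± 1.96 × √(0.925 × 0.075 / 530) = 0.902 to 0.947. This matches 0.92 (0.90, 0.95) in Table 2. That figure takes the HPA as perfect and belongs to Analysis 1. Analysis 2 has no stated figure.

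**2. Parameter count.** With free dependence, population k has the 2×2 table p_k·A + (1−p_k)·B, where A and B are the tables for antibody positives and negatives, with three free cells each. K populations give 6 + K parameters. All K tables lie on one line in three dimensions, and a line has 4 parameters.

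| Data | Rank | Shortfall |
|---|---|---|
| Unknown-prevalence studies only | 4 + K | 2 |
| Plus known positives fixed as antibody positive | 5 + K | 1 |
| Plus known negatives only | 5 + K | 1 |
| Plus both groups | 6 + K | 0 |

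A numerical rank check agrees. At K = 50 there are 56 parameters and the ranks are 54, 55, 55 and 56. Three antibody assays with unrestricted dependence show the same shortfalls: 2 with no known-status group, 1 with known positives, 0 with both groups. Under conditional independence the two-assay model is identified from K = 2 without any known-status group.

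**3. Bounds on specificity with known positives only.** Replacing B by B′ = (1−t)B + tA and p_k by (p_k−t)/(1−t) leaves every table unchanged.

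- *Lower end.* Prevalences must stay non-negative, so t is at most the lowest prevalence. At t = 0.05 the HTK false-positive rate is 0.95 × 0.02 + 0.05 × 0.98 = 0.068, so specificity is 0.932. PPV at 20% is 0.196 / (0.196 + 0.8 × 0.068) = 0.783.
- *Upper end.* Cells of B′ must stay non-negative. The both-positive cell is 0.02 × 0.01 + 0.003 = 0.0032 in B and 0.98 × 0.95 + 0.008 = 0.939 in A, so t is at least −0.0032/0.9358 = −0.00342. The HTK false-positive rate is then 1.00342 × 0.02 − 0.00342 × 0.98 = 0.0167, so specificity is 0.983. PPV at 20% is 0.196 / (0.196 + 0.8 × 0.0167) = 0.936.

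| Lowest study prevalence | HTK specificity | HPA specificity | PPV at 10% | PPV at 20% |
|---|---|---|---|---|
| 0.5% | 0.975-0.983 | 0.985-0.993 | 0.814-0.867 | 0.908-0.936 |
| 2% | 0.961-0.983 | 0.971-0.993 | 0.735-0.867 | 0.862-0.936 |
| 5% | 0.932-0.983 | 0.943-0.993 | 0.616-0.867 | 0.783-0.936 |
| 10% | 0.884-0.983 | 0.896-0.993 | 0.484-0.867 | 0.679-0.936 |

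The lower ends do not depend on the assumed negative-class covariance. The upper end for HTK specificity moves from 0.981 to 0.990 as that covariance goes from 0.001 to 0.009. Requiring positive covariance barely narrows the ranges.

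**4. What known negatives add.** They fix B. HPA results alone are enough, because only one point on the line has the right HPA specificity. If known positives are not fixed as antibody positive, the remaining shortfall of 1 lies in A: specificity stays identified and sensitivity becomes the bounded quantity. If true HTK specificity is 0.98, 500 known negatives run on the HTK give, from those samples alone, 0.98 ± 1.96 × √(0.98 × 0.02/500) = 0.968 to 0.992.

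**5. T-SPOT.** If T-SPOT is independent of the HTK-HPA pair within each class, the model has 8 + K parameters. It is then identified without known negatives: rank 9 of 9 with one population plus known positives, and 10 of 10 with two populations and no known positives.

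**The case against.** A reader might infer that Analysis 2 excludes known negatives and that specificity therefore cannot be estimated at all. The protocol does not support that reading, for four reasons.

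- The source search takes in any study involving the HPA. The HPA is to be chosen on published performance, and validation reports of that kind commonly include negative panels. Known negatives are not named as required, which differs from being ruled out. The section also announces two data routes and shows one item. Text may have been lost there, so no weight is put on the gap.
- Specificity is bounded, and tightly so if a near-zero-prevalence source is included. The wide ranges come from assumed lowest prevalences of 2% and above.
- T-SPOT is in the synthesis, it measures T cells, and the stated dependence covers the HTK and antibody tests only. Conditional independence of T-SPOT would identify the model.
- The quoted sentence is literally true: such studies do contribute information. The Appendix One remark concerns the EuroImmun assay and is not a rule for Analysis 2.

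Priors and the exact form of the dependence may also be set in a statistical analysis plan that is not at hand, so their absence is not held against the protocol.

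These points limit the claim but do not remove it. The protocol itself fixes the focus on unknown-prevalence studies and the dependence in both classes. It requires neither known negatives nor a near-zero-prevalence source, and it does not state independence for T-SPOT, which may follow infection rather than antibody. A restrictive dependence structure or an informative prior would produce an answer, but that assumption would then be supplying it.

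**Conclusion.** The concern holds in limited form. With the named sources and unrestricted HTK-HPA dependence in both classes, HTK and HPA specificity, and hence PPV, are confined to an interval that more two-assay unknown-prevalence studies narrow only if their prevalence is lower than any already included. Within that interval the prior decides.

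The size depends on the lowest study prevalence. At 0.5% the effect is minor and PPV at 20% prevalence stays above 0.90. At 5% PPV runs from 0.78 to 0.94, and the 90% benchmark could appear met or missed on the prior alone. These figures rest on the assumed HPA accuracy and covariances, on the protocol's 98% HTK values, and on known positives being antibody positive. The last is uncertain: the protocol lists as unknown whether every infection produces antibody, and Appendix One puts detection of past disease at about 80%. The shortfall in the parameter count does not depend on the assumed values.

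Analysis 1 and Table 2 are unaffected.

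**What to change.** - **Name known-negative data as a required Analysis 2 source**, with status fixed to antibody negative. The minimum is existing known-negative validation results for the chosen HPA.
- **Do not fix known positives as antibody positive without allowing for non-seroconversion.** Report how the results change with that assumption. Specificity remains identified through the known negatives.
- **Qualify the sentence on unknown-prevalence studies** to say that they bound specificity but do not by themselves identify it under conditional dependence.
- **State any independence assumption relied on**, such as for T-SPOT, and report the sensitivity of specificity and PPV to the priors.
- **Optional:** run the HTK and HPA on archived pre-pandemic plasma.

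The required changes are protocol wording and modelling work, with no new participants. The optional panel costs kits and laboratory time. The downside is that archived or published negatives may differ from current workers, so results should be reported with and without them.

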2) Once the HTKs become available for use and pass the TPP requirements, individuals will be invited to participate in stage two based on a combination of stratified and random sampling, if necessary, based on geography, age, symptom history and EIA result. During this stage, an additional blood sample will be taken. Individuals who complete the HTK will do so independently, and will also take a photograph of their HTK result. Comparative accuracy of reading of HTK results by trained professionals (in the community, and by photograph) will also be explored. Data from this stage will

Evaluating Detection of SARS-CoV-2 antibodies using home test kits (EDSAB-HOME study)

Protocol 30.05.2020 Version 04.03

allow us to assess agreement between user reading, reading of test results by a trained professional in the community and using a photograph, and reading in a laboratory setting. This will allow us to determine whether accuracy estimates from stage one are applicable to these other types of reading. (Objective 2, 3, 5, 6).

All participants will be followed up with weekly symptom questionnaires and linked to routine laboratory and hospital record statistics, to identify progression to severe COVID-19 disease (and possibly mild COVID-19 disease, confirmed microbiologically, depending on changes to future testing strategy) (Objective 4).

In the event that antibody kits are available earlier than expected, and at scale, stage one and two may be combined with all subjects in stage one (above) additionally doing POC tests. In addition, depending on operational capacity, stage two and stage three may also run in parallel.

3) The service evaluation will be extended when the programme expands to home use; however, the evaluation will focus on assessing the usability and accessibility of the programme and to identify any logistical/operational limitations associated with the home delivery system, and where improvements may be required. In addition, the three-stage service evaluation may be extended at a later date to the general population, contingent on sufficient clinical performance of the HTK within the healthcare workers and police officers. (Objective 5)

Figure 1: Overview of the three-stage evaluation study methodology

Recruitment sites and study areas will reside within the UK, and will be chosen based on the epidemiology and operational capacity available during the study launch.

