Evaluating Detection of SARS-CoV-2 antibodies using home test kits (EDSAB-HOME study)

Protocol 30.05.2020 Version 04.03

assume that the accuracy of self-read tests as assessed against expert-read tests is independent of the true antibody status.

In the first analysis, we will examine the probability of a self-read positive result among expert positive results, and the probability of ("false") self-read positive result among expert negatives, both as functions of reported exposure and illness experience, using logistic regression.

The second analysis will estimate the overall Sensitivity of the self-read HTK as Pr(self-read +ve|Expert +ve) x Sensitivity of the Expert-read POC based on the evidence synthesis results (Objective 1, Analysis 2). Similarly the overall specificity of the self-read POC will be estimated as: Pr(self-read -ve|Expert -ve) x Specificity of the Expert-read HTK based on the evidence synthesis results.

Objective 3

To assess whether home photographic recording of HTK is feasible and enhances accuracy of recording relative to user reading;

If possible, we will also compare to results from an automated pixel analysis of a photograph of the test taken by the person tested, and a visual analysis of a photograph taken under optimal conditions in the field. We will report concordance between the methods of interpreting results, and characteristics of discordant results (including whether they are positive or negative using the HPA test).

Objective 4

To determine the acceptability of the tests to the population;

Data (including both quantitative and free text) obtained from the baseline questionnaire on acceptability and usability of the HTK programme completed by participants will be summarised by counts, descriptive statistics and pseudo-anonymised quotes. In addition, work conducted by user researcher team at NHSX and qualitative interviews conducted prior and during the pilot phase of the programme will be included into the results of the evaluation, where appropriate/necessary.

Objective 5

To inform the instructions and other advice to be provided to people undertaking the tests and to those who have a positive and a negative result;

Results obtained on the sensitivity and specificity of the HTK will inform what advice should be given, including whether confirmatory testing using laboratory based tests will be necessary for any subsets of the population, including healthcare workers.

Objective 6

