Sensitivity: The sensitivity of a test refers to the proportion of individuals with the condition who test positive. According to our current understanding:

- Sensitivity of detection rises over time. Median IgG seroconversion was 13 days post duration of symptoms in a large Chinese study (5), compatible with smaller studies (4). By 21-days post symptoms, almost all seroconversion had occurred (5).
- Individuals with severe illness vs. milder clinical illness had higher titres early on (before 14 days) but cases with mild disease achieved similar titres to severe disease later (5).
- The sensitivity of detection of historical COVID-19 disease is probably about 80% (5).

¹ PHE "Evaluation data for Euroimmun IgG ELISA for SARS-CoV-2 antibodies" validation report 28-3-2020, [name]

Evaluating Detection of SARS-CoV-2 antibodies using home test kits (EDSAB-HOME study)

Protocol 30.05.2020 Version 04.03

- Viral mutation is one possible explanation for low sensitivity, especially if very short domains or a small number of peptides are used as antigens (6).
- The sensitivity of diagnosis of SARS-CoV-2 by serological means has not been established in the UK.
- Studies indicate that in people exposed to a household case of COVID-19, a proportion (perhaps 25%) develop antibodies, as detected by anti-S protein EIAs. Whether the other household members were uninfected, or were infected but did not detectable antibody, is unknown (5).

Table 1: Assessment of specificity: sera from historical samples considered low risk for SARS-CoV-2 infection

		Eurolmmun assay result			
Test set	Negative	Indeterminate	Positive	Specificity	
Porton	90	1	1	99%	
Negative					
control set					
(n=92)					

Data extracted from PHE "Evaluation data for Euroimmun IgG ELISA for SARS-CoV-2 antibodies" validation report 28-3-2020, [name]

Table 2: Assessment of sensitivity: sera from known positive cases

	Eurolmmun assay result			
Days post onset	Negative	Indeterminate	Positive	Sensitivity
0-4	18	0	0	0
5-14	18	3	12	46%
15-28	6	1	19	73%
>28	No data			

Data extracted from PHE "Evaluation data for Euroimmun IgG ELISA for SARS-CoV-2 antibodies" validation report 28-3-2020, [name]

Clinical utility

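### Objective 2: the self-read sensitivity and specificity formulas each omit one of two total-probability terms; at the planned 98%/98% the certain shortfall is small

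*Protocol*

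**What the plan says.** Protocol, Statistical Analysis, Objective 2 describes two analyses of user reading. Both "assume that the accuracy of self-read tests as assessed against expert-read tests is independent of the true antibody status".

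The first analysis estimates reading probabilities in both expert strata. For one, "we will examine the probability of a self-read positive result among expert positive results"; for the other, it looks at a "self-read positive result among expert negatives, both as functions of reported exposure and illness experience, using logistic regression".

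The second analysis turns these into accuracy against antibody status. Sensitivity is the "overall Sensitivity of the self-read HTK as Pr(self-read +ve|Expert +ve) x Sensitivity of the Expert-read POC", the latter taken from the evidence synthesis (Objective 1, Analysis 2). Specificity is "Pr(self-read -ve|Expert -ve) x Specificity of the Expert-read HTK based on the evidence synthesis results".

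Two other places bear on the point. Under Three stages, participants are invited to stage two "based on a combination of stratified and random sampling, if necessary, based on geography, age, symptom history and EIA result". The stage two workflow (step 10) runs the HPA on blood taken at the same visit as the kit.

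**The concern.** An antibody-positive person can end with a positive user reading in two ways: the expert reading is positive and the user agrees, or the expert reading is falsely negative and the user nonetheless reads positive. The sensitivity formula counts only the first route. The specificity formula likewise leaves out antibody-negative people whose kit is expert-read positive but user-read negative. The independence assumption does not make either route impossible, so the estimators are incomplete on the protocol's own terms.

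The independence assumption raises a separate and conditional question. If it fails, the probability of a user reading given an expert reading is a mixture over antibody-positive and antibody-negative people. It then depends on who is sampled into stage two, and the protocol allows that to be set partly by EIA result.

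User-read accuracy is part of Objective 2 and is Expected outcome 2. Under Objective 5, kit sensitivity and specificity inform the advice to users and the need for confirmatory testing.

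**Working it through.** **Inputs.** Expert-read Se = Sp = 0.98, the planning values (sample size for Analysis 1 of Objective 1). The protocol gives no reading-error rates. The ranges Pr(S+|E+) = 0.90 to 0.98 and Pr(S+|E-) = 0.01 to 0.10 are assumptions.

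**The plan's own figure.** The protocol states no number for self-read accuracy. The nearest figure that uses these inputs is Table 2 at n = 2,500 and 20% prevalence: PPV 0.92 (0.90, 0.95). PPV = 0.2 × 0.98 / (0.2 × 0.98 + 0.8 × 0.02) = 0.196/0.212 = 0.9245. With 2,500 × 0.212 = 530 expected positives, the Wald interval is 0.9245 ± 1.96 × √(0.9245 × 0.0755/530) = 0.902 to 0.947. It reproduces.

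**Step 1: the formulas under independence.** Let D be true antibody status. Independence means Pr(S|E, D) = Pr(S|E). Then:

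- Se_self = Pr(S+|D+) = Pr(S+|E+) Se + Pr(S+|E-) (1-Se)
- Sp_self = Pr(S-|D-) = Pr(S-|E-) Sp + Pr(S-|E+) (1-Sp)

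The plan keeps only the first term of each. The shortfalls are Pr(S+|E-)(1-Se) and Pr(S-|E+)(1-Sp). Neither is ever negative. Each is zero only if the kit makes no error of that type or users never make the matching misread.

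**Step 2: size at the planning values.** With Pr(S+|E+) = 0.95 and Pr(S+|E-) = 0.02:

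- Sensitivity: plan 0.95 × 0.98 = 0.9310; full 0.9310 + 0.02 × 0.02 = 0.9314.
- Specificity: plan 0.98 × 0.98 = 0.9604; full 0.9604 + 0.05 × 0.02 = 0.9614.

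Over the assumed ranges:

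- Sensitivity shortfall: 0.02 × 0.01 = 0.0002 to 0.02 × 0.10 = 0.0020, or 0.02 to 0.20 points.
- Specificity shortfall: 0.02 × 0.02 = 0.0004 to 0.02 × 0.10 = 0.0020, or 0.04 to 0.20 points.

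For scale, sampling error for sensitivity with 500 positives (2,500 at 20%) is ± 1.96 × √(0.98 × 0.02/500) = ± 1.2 points.

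**Step 3: what happens if independence fails (illustration, all reading rates assumed).** Take Pr(S+|E+) = 0.97 in antibody positives and 0.80 in antibody negatives, and Pr(S+|E-) = 0.10 and 0.02 respectively, with Se = Sp = 0.98. True self-read sensitivity is 0.97 × 0.98 + 0.10 × 0.02 = 0.9526. At 20% antibody positives, the pooled Pr(S+|E+) is (0.97 × 0.196 + 0.80 × 0.016)/0.212 = 0.9572, so the plan gives 0.9572 × 0.98 = 0.938.

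| Antibody positives in stage two | True Se_self | Plan | Two terms, pooled rates |
|---|---|---|---|
| 20% | 0.953 | 0.938 | 0.938 |
| 10% | 0.953 | 0.925 | 0.925 |
| 5% | 0.953 | 0.904 | 0.904 |

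The true value does not move with the mix, but the estimate does, and adding the second term with pooled rates does not repair it. When the reading rates are instead the same in both groups (0.97 and 0.02), the two-term formula returns the true 0.9510 at every mix and the plan gives 0.9506.

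**The case against.** The strongest reply is that the certain error is negligible. At 98%/98% it is at most 0.2 points over the assumed ranges, against about ± 1.2 points of sampling error, and wider if only some participants return for stage two. It also errs towards understating user accuracy. This stands, and it limits the weight of the point. It does not make the formula right, and the correction is nearly free.

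A reader might infer several stronger things that the documents do not support:

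- **That the formulas are wrong whatever the data.** They are exact if the kit makes no error of the relevant type, or if users never make the matching misread.
- **That the loss is 2 points.** This needs Se = 0.80 with 10% false-positive reads (0.20 × 0.10 = 0.020). Appendix One's figure of about 80% concerns detection of past disease, whereas Objective 2 targets antibody status. By default, stage two follows only once the kit passes its target product profile, and the protocol gives 98% as the regulator's minimum at the time. The profile was still under consultation and stages one and two may be combined, so lower values are possible, but they are not the base case.
- **That the independence assumption is shown to be false.** It is declared openly, and the documents contain no data against it. Modelling reading error by exposure and illness sits awkwardly with it, but that model could also reveal a failure. Objective 3 will report whether discordant readings are HPA positive or negative, which is a partial check. Automated reading or swapped tests deal with readers who know their own status, though not with any dependence carried by the kit itself.
- **That a direct table of user reading against HPA removes the problem.** Analysis 2 says the assumption of an error-free laboratory assay is known to be untrue, so such a table imports reference error. Taking Se and Sp from the evidence synthesis is a reasoned choice.

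**Conclusion.** The point holds in a limited form. Both self-read formulas are incomplete as written, even under the protocol's own assumption, and understate user-read accuracy whenever both the expert-read kit and the user make errors. At the planned 98%/98% and assumed misread rates of 1-10%, the shortfall is about 0.02 to 0.2 points. It scales with 1-Se or 1-Sp if the kit performs worse.

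The bias from a failure of independence could be larger and would depend on the stage-two antibody mix. It is conditional, and its size is unknown. The table above shows the mechanism and is not an estimate. A claim that user-read accuracy will be seriously biased goes beyond the documents.

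**What to change.** Replace both products with the two-term expressions. Pr(S+|E-) comes directly from the first analysis, and Pr(S-|E+) is one minus its other probability. Compute the sums inside the Bayesian model so that the intervals carry the uncertainty in all components. This costs a change of wording and a few lines of code, with no new data.

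Add a sensitivity analysis that relaxes independence: let Pr(user read | expert read) differ by HPA or latent-class antibody status, and combine within status. The HPA result from the same visit is already planned. The cost is sparse cells and wider intervals: even if all 2,500 took part at 20% prevalence, a 98% sensitive kit would leave only about 500 × 0.02 = 10 antibody-positive people with a negative expert reading.

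If a direct table of user reading against HPA is reported, label it as a check only, because the HPA is an imperfect reference.
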